## 5.1.4 Primary Hypothesis

[figure not shown]
The primary endpoint is the Day 28 CR rate among all patients. Historical control data indicates a Day 28 CR rate of 25-30% is expected under currently available treatment strategies for SR-aGVHD. The primary hypothesis is that the Day 28 CR rate under T-Guard treatment will be superior to historical rates. This will be evaluated by comparing the null hypothesis that the Day 28 CR rate under T-Guard treatment is 30% to the alternative hypothesis that this rate exceeds 30% using a one-sided test at a significance level of 2.5%.

# 5.1.5 Sample Size and Power Considerations

Based on the results of the Phase I/II study (Groth, van Groningen et al. 2018), we expect a Day 28 CR rate of 50% under T-Guard treatment. A literature review suggests a Day 28 CR rate of 25-30% in historical controls, summarized below:

- A random-effects meta-analysis of the 11 prospective studies on second line treatment for aGVHD reported in Martin et al. 2012 (see Figure 5-1) resulted in a CR rate of 29.5% (95% CI 24.0 – 35.3%). However, in seven of the 11 studies CRs that were achieved after Day 28 were included, and one study used CR assessment shorter than 28 days. In addition, eight of the 11 studies did not specify whether addition of another therapy to the protocol-defined treatments would result in classification of response as a nonresponder.
- The recently published REACH1 study (Jagasia, Zeiser et al. 2018) with the JAK 1/2 inhibitor ruxolitinib (Jakafi/Jakavi) resulted in a CR rate at Day 28 of 26.8%.
- A meta-analysis of the 20 T-Guard treated patients of the Phase I/II study, 42 institutional control patients from that study's two centers, 77 matched control patients from the MAGIC database, and 71 patients from the REACH1 study resulted in Day 28 CR rates of 49.6% (95% CI 28.8 70.4%) in the T-Guard patients and 23.0% (95% CI 17.2 28.9%) in the control patients, adjusted for Harris acute GVHD grade (Table 5-1). CR rates were adjusted at the same ratio as observed in the T-Guard arm (3:10:7 for grades II:III:IV) using a generalized linear model adjusted for Harris grade and data source (Phase I/II, institutional controls / MAGIC / REACH1).

## Figure 5-1: Forest Plot of CR Rates from the Meta-analysis on Second Line aGVHD Therapy from (Martin, Rizzo et al. 2012) [numbers next to study treatment name refer to the references in that paper].

Harris Grade	Phase I/II T- Guard arm	Combined controls	Institutional controls	MAGIC controls	REACH1 study
			 controis		-
	2/3 (66.7%)	17/35 (48.6%)	-	6/12 (50.0%)	11/23 (47.8%)
III	5/10 (50.0%)	19/88 (21.6%)	3/20 (15.0%)	9/34 (26.5%)	7/34 (20.6%)
IV	3/7 (42.9%)	10/67 (14.9%)	5/22 (22.7%)	4/31 (12.9%)	1/14 (7.1%)
All	10/20 (50.0%)	46/190 (24.2%)	8/42 (19.0%)	19/77 (24.7%)	19/71 (26.8%)
Adjusted CR Rate (95% CI)	49.6% (28.8 – 70.4%)	23.0% (17.2 – 28.9%)	25.7% (13.2 – 38.2%)	20.2% (10.5 – 29.8%)	24.6% (15.4 – 33.8%)

# Table 5-1: Observed and Adjusted Day 28 CR Rates from Meta-analysis of Phase I/II Study, MAGIC Controls, and REACH1 Study

The primary hypothesis will be evaluated by comparing the proportion of patients attaining a Day 28 CR to a historical rate of 30%, targeting 80% power to see a CR rate of 50% under T-Guard treatment. In addition, one interim analysis for futility will be incorporated. To generate the required sample size and futility and efficacy boundaries for this test, we used a Simon's two-stage minimax design. A sample size of 47 patients is required under this design to compare a null rate of 30% to an alternative rate of 50% with a one-sided type I error rate of 2.5% and 80% power.

# 5.2 INTERIM ANALYSIS AND STOPPING GUIDELINES

## 5.2.1 Interim Analysis for Futility

This trial will include one interim analysis for futility. At the interim analysis, the number of Day 28 CRs will be compared to a futility boundary determined by Simon's two-stage minimax design comparing a null rate of 30% to an alternative rate of 50% with a one-sided type I error rate of 2.5% and 80% power. This is a non-binding stopping rule, in that the type I error rate will be controlled at 2.5% even if the rule is not followed exactly. If the number of CRs fails to exceed the boundary, the DSMB will be consulted on the appropriate course of action, including whether to declare futility and close the trial early.

The futility boundaries and operating characteristics of this design are displayed in Table 5- 2A. The interim analysis will be conducted when 21 patients are evaluable for Day 28 CR. If the number of CRs is 6 or below, the boundary is crossed. At the final analysis, the futility boundary is 20 CRs and efficacy is declared only if the observed number of CRs exceeds this boundary, i.e. the observed rate is at least 21/47 (44.6%).

# Table 5-2A: Single Boundary Non-Binding Futility Stopping Thresholds from Simon'sTwo-stage Minimax Design with One-Sided Type I Error 2.5% and Power 80%

Analysis	Number of Evaluable	Futility Boundary -	Probability of S Under True C	
	Patients	# of CRs (CR rate)	30%	50%
Interim	21	6 (28.5%)	55.1%	3.9%
Final	47	20 (42.6%)	-	-

# 5.2.2 Guidelines for Safety Monitoring

Monitoring of key safety endpoints will be conducted monthly, and if their rates significantly exceed pre-set thresholds, the NHLBI will be notified in order that the DSMB can be advised. Policies and composition of the DSMB are described in the BMT CTN's Manual of Procedures. These stopping guidelines serve as triggers for consultation with the DSMB for additional review and are not formal "stopping rules" that mandate automatic closure of study enrollment. The number of enrolled patients that fail to receive any T-Guard treatment and the occurrence of toxicity, adverse events, and other safety endpoints will be monitored regularly. These data will be reported to the DSMB at semi-annual meetings at a minimum; in the event that any safety concerns arise, these data will be conveyed to the DSMB expeditiously. Additionally, the DSMB will conduct a full review of study endpoint and safety data after 10 and 30 participants are evaluable for Day 28 CR.

[figure not shown]
One key safety endpoint for this study is Day 30 overall mortality. The rate of mortality within 30 days following T-Guard initiation will be monitored in patients who initiate this treatment. Based on historical data from MAGIC, the expected probability of Day 30 mortality in SR- aGVHD patients after initiating second line treatment is 15%, while a rate of 30% is considered to be unacceptable. A sequential probability ratio test (SPRT) for binary data that compares a rate of 15% under the null hypothesis to a rate of 30% under the alternative hypothesis will be used for monthly monitoring of the Day 30 overall mortality rate in this study.

This sequential testing procedure preserves the type I error rate at a prespecified level across all of the monthly examinations. The binary SPRT can be represented graphically. At each month, the number of evaluable patients is plotted against the cumulative number of events.

The continuation region of the SPRT is defined by two parallel lines. Only the upper boundary will be used for monitoring in order to protect against excessive Day 30 mortality. If the cumulative number of deaths falls above the upper boundary the SPRT rejects the null hypothesis and concludes that more deaths occurred than should be expected in the observed number of evaluable patients. Otherwise, the SPRT continues until enrollment reaches the target sample size of 47 patients. The SPRT can be displayed in a tabular form, as shown in Table 5-2B. This table gives the rejection boundaries for the number of Day 30 mortality events corresponding to the number of evaluable patients. At least three deaths must be observed in order to trigger review. Figure 5-2A displays the same information in a graphical format.

Number of Evaluable Patients	Rejection Boundary for Number of Day 30 Deaths
1-2	
3-5	3
6-10	4
11-14	5
15-19	6
20-24	7
25-28	8
29-33	9
34-37	10
38-42	11
43-46	12
47	13

Figure 5-2A: Rejection Boundary for Day 30 Overall Mortality Monitoring in 47 Patients

The actual operating characteristics of the truncated test are shown in Table 5-2C, obtained from a simulation study that assumed uniform accrual of 47 patients over a 365-day period with 395 days of monitoring.

True Day 30 Mortality Rate	15%	20%	25%	30%
Probability Reject Null	0.096	0.299	0.579	0.814
Mean Month Stopped	12.3	11.0	9.2	7.3
Mean # Deaths by Day 30	6.6	7.9	8.1	7.4
Mean # Patients Enrolled	44.7	40.5	34.4	27.9

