# Table 5-2C: Operating Characteristics of the Binary SPRT for Day 30 Overall Mortalityfrom a Simulation Study with 100,000 Replicates

The testing procedure rejects the null hypothesis in favor of the alternative 9.6% of the time when the true Day 30 mortality rate is 15% and 81.4% of the time when the rate is 30%. This corresponds to a type I error rate of 9.6% and a type II error rate of 18.6%. If the true Day 30 mortality rate is 30%, the DSMB will be consulted 220 days after opening on average, when 7 events have been observed in 28 patients.

CTCAE Grade 4 or higher capillary leak syndrome (CLS) is another key safety endpoint that will be monitored during this study. The rate of Grade 4 or higher CLS occurring within 30 days following T-Guard initiation will be monitored in patients who initiate this treatment. This monitoring will compare a null rate of 5% to an alternative rate of 15%, considered to be unacceptable, using a sequential probability ratio test (SPRT) for binary data. The SPRT can be displayed in a tabular form, as shown in Table 5-2D. This table gives the rejection boundaries for the number of Day 30 CLS events corresponding to the number of evaluable patients. At least two events must be observed in order to trigger review. Figure 5-2B displays the same information in a graphical format.

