# Table 5-2D: Sequential Monitoring Plan of Day 30 Grade 4 or Higher Capillary LeakSyndrome in 47 Patients

Number of Evaluable Patients	Rejection Boundary for Number of Day 30 Events
1	
2-7	2
8-18	3
19-29	4
30-39	5
40-47	6

The actual operating characteristics of the truncated test are shown in Table 5-2E, obtained from a simulation study that assumed uniform accrual of 47 patients over a 365-day period with 395 days of monitoring.

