# Table 5-2E: Operating Characteristics of the Binary SPRT for Day 30 Grade 4 or Higher Capillary Leak Syndrome from a Simulation Study with 100,000 Replicates

True Day 30 Grade 4 or Higher CLS Rate	5%	10%	15%	20%
Probability Reject Null	0.094	0.466	0.807	0.954
Mean Month Stopped	12.3	9.9	7.3	5.4
Mean # CLS events by Day 30	2.2	3.5	3.7	3.5
Mean # Patients Enrolled	44.7	36.8	27.8	21.1

The testing procedure rejects the null hypothesis in favor of the alternative 9.4% of the time when the true Day 30 Grade 4 or higher CLS rate is 5% and 80.7% of the time when the rate is 15%. This corresponds to a type I error rate of 9.7% and a type II error rate of 19.3%. If the true Day 30 Grade 4 or higher CLS rate is 15%, the DSMB will be consulted 220 days after opening on average, when 4 events have been observed in 28 patients.

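### Section 5.2.2 ends the mortality SPRT at the 47th enrollment, but its boundary tables and stated error rates assume monitoring until all 47 patients reach Day 30

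*Combined protocol and SAP*

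**What the plan says.** Section 5.2.2 sets up two sequential probability ratio tests, one for Day 30 mortality (15% against 30%) and one for Grade 4 or higher CLS by Day 30 (5% against 15%). On timing it says "Monitoring of key safety endpoints will be conducted monthly". For mortality, if the upper boundary is not crossed, "Otherwise, the SPRT continues until enrollment reaches the target sample size of 47 patients".

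Tables 5-2B and 5-2D give the boundaries by number of evaluable patients, up to 47. Table 5-2B has a separate last row for exactly 47 evaluable patients (13 deaths). The operating characteristics of the mortality rule come from a "simulation study that assumed uniform accrual of 47 patients over a 365-day period with 395 days of monitoring", and the text under Table 5-2D gives the same basis for CLS. From these runs the protocol states type II errors of 18.6% for mortality at a true 30% rate (Table 5-2C) and 19.3% for CLS at a true 15% rate (Table 5-2E).

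The CLS paragraphs contain no sentence on when monitoring ends.

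**The concern.** A patient who has just been enrolled is not yet evaluable for a Day 30 endpoint. A rule that stops when the 47th patient enters can therefore never see 47 evaluable patients, and it loses the looks at about Day 365 and Day 395. The tables and the simulation need those looks.

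A team that follows the sentence would run a less sensitive rule than the one whose error rates the DSMB and IRB have been given. Those rates tell them how likely the trigger is to fire if early mortality or severe CLS is at the level the protocol calls unacceptable.

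**Working it through.** **Inputs, all from 5.2.2.** 47 entries uniform over 365 days; monthly looks; 395 days of monitoring; the boundaries of Tables 5-2B and 5-2D. Two assumptions were added: looks fall every 365/12 = 30.4 days (13 looks, the last at about Day 395), and a patient is counted at entry + 30 days. The second fits the endpoint as worded ("The rate of Grade 4 or higher CLS occurring within 30 days following T-Guard initiation will be monitored") and reproduces the CLS table.

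**What the literal ending removes.**
- Expected day of the last entry: 365 × 47/48 = Day 357.
- Look 11, Day 334.6: expected evaluable = 47 × (334.6 − 30)/365 = 39.2.
- Look 12, Day 365: enrollment is complete; expected evaluable = 47 × 335/365 = 43.1.
- Look 13, about Day 395: all 47 evaluable.

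So the last look with fewer than 47 enrolled is usually look 11, with about 39 evaluable. The last row of Table 5-2B is never reached.

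**Probability of a trigger.** 200,000 simulated trials per rate, trigger when events ≥ tabled boundary:

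| Rule, true rate | Printed | Looks to Day 395 | Looks to Day 365 | Only looks with fewer than 47 enrolled |
|---|---|---|---|---|
| Mortality 15% | 0.096 | 0.104 | 0.103 | 0.099 |
| Mortality 20% | 0.299 | 0.316 | 0.310 | 0.294 |
| Mortality 25% | 0.579 | 0.595 | 0.584 | 0.556 |
| Mortality 30% | 0.814 | 0.822 | 0.810 | 0.782 |
| CLS 5% | 0.094 | 0.096 | 0.092 | 0.090 |
| CLS 10% | 0.466 | 0.465 | 0.438 | 0.422 |
| CLS 15% | 0.807 | 0.805 | 0.771 | 0.749 |
| CLS 20% | 0.954 | 0.954 | 0.937 | 0.923 |

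**Reproduction.** With looks to about Day 395 the CLS column matches Table 5-2E closely. At 15% the mean month stopped (7.29 against 7.3) and mean enrolled (27.9 against 27.8) match as well. The mortality column is within 2 points of Table 5-2C but not exact.

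**Type II error, 1 − probability of a trigger.**
- Mortality at 30%: 1 − 0.822 = 17.8% to Day 395; 1 − 0.810 = 19.0% to Day 365; 1 − 0.782 = 21.8% under the literal ending. Stated: 18.6%.
- CLS at 15%: 1 − 0.805 = 19.5% to Day 395; 1 − 0.771 = 22.9% to Day 365; 1 − 0.749 = 25.1% under the literal ending. Stated: 19.3%.

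**Calibration of the mortality run.** The printed mortality boundary equals floor(1.73 + s·n) + 1, with s = ln(0.85/0.70)/ln[(0.30 × 0.85)/(0.15 × 0.70)] = 0.219. Raising the intercept to 1.82 brings the full run to 0.095 at 15% and 0.815 at 30%, close to the printed 0.096 and 0.814. The literal ending then gives 0.771 at 30%. The loss is about 4 points with either intercept.

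**The case against.** The strongest reply is that the plan has already settled the matter. The 395 days are stated beside both tables, 395 = 365 + 30, and the boundaries are indexed by evaluable patients up to 47. On that reading the sentence merely names the truncation size of the test. This is probably what was meant, and it is why the remedy is a wording change. It does not make the sentence correct: as written, it fixes an ending under which the last row of Table 5-2B cannot be used.

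A reader might go further and infer that 81.4% and 80.7% overstate detection while accrual can still be stopped. The documents do not support that. They present the figures as the probability that the procedure rejects over the disclosed 395 days, and nowhere call them detection before accrual closes.

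Nor does it follow that looks after the 47th entry protect no one. Dosing is planned over Days 0 to 6 and may extend to 14 days. Under uniform accrual the last patient is within 6 days of starting at Day 365 with probability 1 − (359/365)^47 = 54%, and within 14 days with probability 1 − (351/365)^47 = 84%. Counting the Day 365 look nearly closes the mortality gap (0.810 against 0.814 printed).

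Three further limits stand:
- The sentence sits only in the mortality paragraph, so the CLS figures apply by parallel.
- The size depends on conventions. Evenly spaced entry or 30-day months gives about 0.76 to 0.785 for CLS before full enrollment. If events count as soon as they occur, CLS is 0.79 to 0.81 and mortality 0.84 to 0.86, so the shortfall largely or wholly goes; that variant does not reproduce the printed CLS type I error (about 0.11 against 0.094).
- The rules prompt DSMB consultation and do not close the trial. The DSMB also reviews full data after 10 and 30 evaluable patients and meets at least semi-annually.

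**Conclusion.** The inconsistency is real and small. Section 5.2.2 gives two endings for the mortality rule, and the stated error rates go with the one its sentence does not describe. Followed literally, the sentence raises the mortality type II error at a true 30% rate to about 22%, roughly 4 points above the same boundaries run to Day 395. The same ending applied to CLS gives about 25% at a true 15% rate, or about 23% with the Day 365 look.

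These sizes rest on uniform accrual over 365 days, monthly looks and patients counted at Day 30. The simulation behind the printed tables is not in question, and no boundary, sample size or efficacy conclusion is affected.

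**What to change.** In 5.2.2, replace the sentence on when the SPRT ends with one that covers both rules, for example: *For both the mortality and the CLS rule, monitoring continues until all 47 treated patients are evaluable at Day 30.* Keep the boundaries and the 395-day operating characteristics, which then describe the rule as written. The cost is one sentence, with no new analysis.

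Optionally, add a row to Tables 5-2C and 5-2E for the probability of a trigger before enrollment completes: about 78% for mortality at a true 30% rate and about 75% for CLS at a true 15% rate, under uniform accrual with patients counted at Day 30. That needs one rerun of the existing simulation and is a reporting preference.

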# Table 5-2C: Operating Characteristics of the Binary SPRT for Day 30 Overall Mortalityfrom a Simulation Study with 100,000 Replicates

The testing procedure rejects the null hypothesis in favor of the alternative 9.6% of the time when the true Day 30 mortality rate is 15% and 81.4% of the time when the rate is 30%. This corresponds to a type I error rate of 9.6% and a type II error rate of 18.6%. If the true Day 30 mortality rate is 30%, the DSMB will be consulted 220 days after opening on average, when 7 events have been observed in 28 patients.

CTCAE Grade 4 or higher capillary leak syndrome (CLS) is another key safety endpoint that will be monitored during this study. The rate of Grade 4 or higher CLS occurring within 30 days following T-Guard initiation will be monitored in patients who initiate this treatment. This monitoring will compare a null rate of 5% to an alternative rate of 15%, considered to be unacceptable, using a sequential probability ratio test (SPRT) for binary data. The SPRT can be displayed in a tabular form, as shown in Table 5-2D. This table gives the rejection boundaries for the number of Day 30 CLS events corresponding to the number of evaluable patients. At least two events must be observed in order to trigger review. Figure 5-2B displays the same information in a graphical format.

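### The Day 30 mortality boundaries in Table 5-2B and the operating characteristics in Table 5-2C probably describe slightly different rules, and the capillary leak type I error is given as both 9.4% and 9.7%

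*Combined protocol and SAP*

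**What the plan says.** Section 5.2.2 sets up two SPRTs, one for Day 30 mortality and one for Grade 4 or higher CLS by Day 30.

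- **Hypotheses and looks.** The mortality test "compares a rate of 15% under the null hypothesis to a rate of 30% under the alternative hypothesis". "Monitoring of key safety endpoints will be conducted monthly".
- **Direction.** "Only the upper boundary will be used for monitoring in order to protect against excessive Day 30 mortality". "At least three deaths must be observed in order to trigger review", so reaching the tabled count is itself a crossing.
- **Boundaries.** Table 5-2B lists the counts under "Rejection Boundary for Number of Day 30 Deaths"; Table 5-2D does the same for CLS.
- **Operating characteristics.** For both rules these come from a "simulation study that assumed uniform accrual of 47 patients over a 365-day period with 395 days of monitoring", with 100,000 replicates (Tables 5-2C and 5-2E). For mortality the text says that the procedure "rejects the null hypothesis in favor of the alternative 9.6% of the time when the true Day 30 mortality rate is 15" percent. It gives type I error 9.6% and type II error 18.6%, and at a true rate of 30% consultation after 220 days on average, with 28 patients.
- **CLS error rates.** Table 5-2E (0.094) and the first sentence below it give 9.4% rejection at the 5% null rate. The next sentence says: "This corresponds to a type I error rate of 9.7% and a type II error rate of 19.3" percent.

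The section says the type I error is held at a level fixed in advance, but states neither that level nor the SPRT's nominal alpha and beta.

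**The concern.** A boundary table and its operating characteristics should be two views of one rule. Here the printed mortality counts appear to trigger more often than Table 5-2C says. If a different set of counts was simulated, the DSMB has been shown the properties of a rule other than the one it would apply. Someone working from the simulated rule and someone working from Table 5-2B could then disagree on whether 4 deaths in 10 patients, 7 in 24, 9 in 33 or 11 in 42 is a crossing. The two CLS figures are one quantity given two values.

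**Working it through.** **Inputs (all from Section 5.2.2).** 47 patients; uniform accrual over 365 days; monitoring to Day 395 with monthly looks; upper boundary only; mortality boundaries for evaluable n of 3-5: 3, 6-10: 4, 11-14: 5, 15-19: 6, 20-24: 7, 25-28: 8, 29-33: 9, 34-37: 10, 38-42: 11, 43-46: 12, 47: 13. CLS boundaries for n of 2-7: 2, 8-18: 3, 19-29: 4, 30-39: 5, 40-47: 6.

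**Model.** Entry times are random uniform on 0 to 365 days. A patient is evaluable 30 days after entry. There are 13 looks, and the rule rejects when events reach the tabled count. There were 1,000,000 replicates per rate.

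**Step 1: reproduce the plan's CLS results (Table 5-2D boundaries).**

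| True CLS rate | 5% | 10% | 15% | 20% |
|---|---|---|---|---|
| Table 5-2E, rejection | 0.094 | 0.466 | 0.807 | 0.954 |
| Simulated | 0.0955 | 0.465 | 0.807 | 0.954 |
| Table 5-2E, mean enrolled | 44.7 | 36.8 | 27.8 | 21.1 |
| Simulated | 44.7 | 36.9 | 27.9 | 21.1 |

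Mean months also agree (12.3, 9.9, 7.3, 5.4). The set-up therefore fits the plan's own simulation.

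**Step 2: the same code on the mortality boundaries.**

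| True mortality rate | 15% | 20% | 25% | 30% |
|---|---|---|---|---|
| Table 5-2C, rejection | 0.096 | 0.299 | 0.579 | 0.814 |
| Table 5-2B as printed | 0.105 | 0.315 | 0.596 | 0.824 |
| One death higher at n = 10, 24, 33, 42 | 0.096 | 0.299 | 0.580 | 0.815 |
| Table 5-2C, mean month | 12.3 | 11.0 | 9.2 | 7.3 |
| Table 5-2B as printed | 12.2 | 10.9 | 9.0 | 7.1 |
| One death higher at those four | 12.3 | 11.0 | 9.2 | 7.3 |
| Table 5-2C, mean enrolled | 44.7 | 40.5 | 34.4 | 27.9 |
| Table 5-2B as printed | 44.5 | 40.1 | 33.8 | 27.3 |
| One death higher at those four | 44.7 | 40.5 | 34.4 | 27.9 |

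With 100,000 replicates the standard error at 0.096 is sqrt(0.096 × 0.904 / 100,000) = 0.0009. The null-rate gap is 0.105 − 0.096 = 0.009, nine to ten standard errors, so it is not simulation noise. Type II error for the printed boundaries is 1 − 0.824 or 0.825 (runs differ in the third decimal), about 17.5%. The mean stop at 30% is 7.1 × 395/13 ≈ 215 days, against 220 stated.

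**Step 3: where the difference may come from.** The SPRT boundary is a line, intercept + slope × n.

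- Log odds ratio: ln[(0.30 × 0.85)/(0.15 × 0.70)] = 0.8873.
- Slope: ln(0.85/0.70)/0.8873 = 0.2188.
- Intercept if (1 − beta)/alpha = 5: ln(5)/0.8873 = 1.814.

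At n = 10, 24, 33 and 42 this line stands at 4.002, 7.065, 9.035 and 11.004. Each is just above an integer, so one more death is needed than Table 5-2B prints. At the other sample sizes from 3 up the counts agree. Table 5-2B itself implies an intercept between 5 − 15 × 0.2188 = 1.718 and 7 − 24 × 0.2188 = 1.748, which excludes 1.814. The same ln(5) with the CLS rates (slope 0.0919, intercept 1.330) gives every boundary in Table 5-2D. The ratio of 5 is an inference; the documents do not state it.

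**Step 4: CLS type I error.** Both 9.4% and 9.7% are given for the same quantity. The simulated 9.55% lies midway, about 1.6 standard errors (0.0009 each) from either.

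**The case against.** The strongest objection is that uniform accrual can also mean evenly spaced entry. With patient k entering at k × 365/47 days, the printed boundaries give 0.096, 0.298, 0.578 and 0.812, with 44.8, 40.5, 34.3 and 27.9 enrolled, close to Table 5-2C. It is therefore not proven that the printed boundaries were never simulated. But that model misses the mean-month row (11.1, 9.3 and 7.4 at 20, 25 and 30%, against 11.0, 9.2 and 7.3). It also fails the CLS table, which the plan states under the same accrual assumption: about 0.103 against 0.094 at the 5% rate, and 27.1 enrolled against 27.8 at 15%. Placing entries at interval midpoints gives 9.9% for mortality. No single accrual model tried fits both tables with the printed boundaries.

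Three further objections stand. The ln(5) line was found by fitting, and two of its four differing cells turn on thousandths, so it cannot serve as a source of replacement counts. A reader might infer that 10.5% breaches a 10% limit, but no such limit is stated. A reader might also infer that 9.4% is proven and 9.7% wrong; simulation cannot decide, and 9.4% is favoured only because the table and the adjacent sentence agree on it.

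**Conclusion.** Wrong as written, with low materiality. Under the accrual model that reproduces the CLS results, the printed mortality boundaries have a type I error of about 10.5% rather than 9.6% and a type II error of about 17.5% rather than 18.6%. The trigger probability is understated by 0.9 to 1.7 points across the tabled rates. Tables 5-2B and 5-2C probably describe slightly different rules. This rests on random uniform entry, 13 monthly looks and evaluability at Day 30.

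The CLS contradiction needs no assumption, since both figures are printed.

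It would be too strong to read this as a failure of safety monitoring. The printed rule is slightly more cautious than described. Section 5.2.2 makes a crossing a prompt for DSMB consultation, not automatic closure, and adds full DSMB reviews after 10 and 30 evaluable participants. The primary efficacy test is unaffected.

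**What to change.** 1. State the nominal alpha and beta of both SPRTs and the accrual model simulated (random or evenly spaced entry, look dates).
2. Make Tables 5-2B and 5-2C and the text below them describe one rule. If the printed boundaries stand, restate rejection as about 0.105, 0.315, 0.596 and 0.824, type I error as about 10.5%, type II as about 17.5%, and consultation at a 30% rate as about 215 days and 27 patients. Otherwise the sponsor should print the boundaries it actually simulated. That choice is the sponsor's, and no trigger counts are proposed here.
3. Reconcile the CLS 9.7% with the 9.4% in Table 5-2E and the adjoining sentence.

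The cost is a rerun of an existing simulation plus table and text edits. Sample size, visits and data collection do not change.
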